APPENDIX

Appendix A: Process evaluation topic guides

IPT participating adolescents' topic guide on implementation and CMOs

THEMES	PROBES
Thank you for agreeing to be interviewed. We would like to	
understand your experience of IPT. Understanding this might	
help us to make IPT better for adolescents in the future. Please	
be open with us. There are no right or wrong answers, and we	
will not be offended if you tell us anything negative about IPT.	
Your experience is very important which is why we are here	
today.	
Accessing IPT (Barriers & Facilitators)	
How did you decide to join IPT?	Did you consult with your parents or friends to make a decision? If so, what were
	their suggestions?
	Did you have any concerns about joining? Did you worry about stigma, missing
	classes?
	How did you decide at the end to join?
Attending IPT (Barriers & Facilitators)	
How was your experience attending the Sessions?	

and the large later and the large later					
Vhat made it difficult to attend the sessions each week?	Stigma, missing out on chores/schoolwork/leisure activities/timing/commute				
Vhat made it easier to attend the sessions each week?	Sessions being in school/timing/peers joining/school support/parent support				
Online sessions (Did you participate in a virtual session?)					
compared to the face to face group sessions what did you think	What did you like? What did you dislike?				
f the online sessions?					
low easy or difficult was it for you to join the virtual sessions?	Access to a phone, privacy in your home, internet connection, noise				
Vhy?					
low can we improve the online sessions?					
Mechanism of IPT					
Vhat did you think of IPT?	What did you like and dislike? And why?				
enefit Mechanisms					
What type of problems do you think IPT helped you with? (ask for	Mention a couple: Improved symptoms (e.g., better mood, less guilty, more				
n example) [OUTCOMES]	hopeful), better sleep and appetite, better concentration, improved functioning				
	(e.g., school, social)				
Vhat aspect of IPT helped with this problem ? (ask for an	Mention a couple: Space to heal (sick role), linking events to mood, daily mood				
xample) [INTERVENTION PROCESSES AND ACTIONS]	check, learning communication skills, decision analysis, practice at home, group				
	setting				
low do you think IPT was helpful with those problems?	Reducing interpersonal conflict				
MECHANISM]					
•					
	7) More aware of emotions and able to control them				
n example) [OUTCOMES] What aspect of IPT helped with this problem ? (ask for an xample) [INTERVENTION PROCESSES AND ACTIONS]	hopeful), better sleep and appetite, better concentration, improved function (e.g., school, social) Mention a couple: Space to heal (sick role), linking events to mood, daily months check, learning communication skills, decision analysis, practice at home, grasetting 1) Reducing interpersonal conflict 2) Increasing social support 3) Feeling supported by the group 4) IPT skills use 5) Improved Self Efficacy 6) More hopeful				

During the program, you first had an individual session, then pre-	Do you think this was once you got to talk about your problem area?
group, then 10 group sessions. I am curious, when did you start	
feeling better? Was it after the first session, or towards the end	
of the groups?	
Harm Mechanisms	
You said you did many activities in the group, what parts of IPT	- Groups being held in school, affecting classes
was not helpful to you? (ask for an example) [INTERVENTION	- IPT components (e.g, practice at home, roleplays, strategies)
PROCESSES AND ACTIONS]	
IPT might also have a negative effect on your life. We would like	
to understand this better. What type of negative effects do you	
think it had on your life? [OUTCOMES]	
If yes, how do you think IPT caused these problems?	missing out on work/coursework
[MECHANISMS]	stigma/labelling ruminating over problems
	4) pick up harmful behaviour
Context of IPT	
Now I would like you to think about your own group. How many	- Why?
were you? What were the ages?	
In your IPT group, do you think some kids benefited more than	
others? Do you think some kids did not benefit at all? [CONTEXT]	
Do you think, all kids from all backgrounds can benefit from IPT?	- High SES/Low SES
[CONTEXT]	- Older/younger - Girls/boys
	- (1113/30073

What do you think is necessary for IPT to work? [CONDITIONS]	 Supportive family Supportive school environment Have basic needs met Adversity
Now I want to ask about your school and how it affected your experience of doing IPT. Can you tell me what your teachers thought about you	- Were they supportive or unsupportive, or both? - Why?
can you tell me what your parents thought about your participation in IPT?	-
Now I want to hear about what your classmates - What did they think about you participating in IPT? What help or support did you get from your parents, teachers or	-
classmates when you were participating in IPT? Whilst you were participating in IPT did your parents, teachers or	- How did they affect you?
classmates do any unhelpful things? What were they?	

Caregivers of IPT participating adolescents' topic guide on implementation and CMOs

THEMES	PROBES
Thank you for agreeing to be interviewed. We would like to understand your experience of having	
your child join our program. Please be open with us. There are no right or wrong answers, and we	
will not be offended if you tell us anything negative about the program. What was the name of your	
son/daughter who attended the program? [Write down the NAME. If there were more than one	
adolescent who attended the program, make sure that the answers capture both kids]	
Accessing the program (Barriers & Facilitators)	
What did you think about [NAME] joining the programme?	
Did you have any concerns about [NAME] joining? What were your concerns?	Did you worry about stigma, missing classes?
What made you decide to let them join?	
How do you think we could encourage other caregivers to let their adolescent join a program like	Parent orientationsLived experiences sharing
this?	- Lived experiences sharing
Attending the program (Barriers & Facilitators)	
Adolescents were asked to attend the programme every week. How easy or difficult was it for	
[NAME] to attend every week?	
What were the reasons why [NAME] had to miss sessions?	Missing classes, not attending house chores?
What could we have done differently to make it easier for your [NAME] to attend?	Explained better about the programme?
	Changed the session timing? Incentives?
Mechanism of IPT	

Because this is the first time we are testing the programme in Nepal we care very much about what	What did you like and dislike? Helpful or
parents think about it. What did you think about the programme?	unhelpful? Why?
What type of changes did you see in [NAME] because of their participation in the programme? Do you have an example?	In terms of heart-mind problems (getting better or worsening), School: going to school more frequently, better grades in school (missing school or worse grades)
When did you start seeing those changes?	Did you see benefits (or harm) after the pre- group sessions, or after the first couple of IPT sessions, or towards the end of the sessions?
You said, you saw [REPEAT THE CHANGES THAT THE CAREGIVER MENTIONED HERE]. We are trying	
to understand more about this, to see how and why this program resulted in those changes.	
Did you notice [NAME] use any techniques or skills he learned in the program?	Would [NAME] talk about what was learned in
	the program?
How did [NAME]s relationships change, while he/she was in the program? Can you give us	Can you tell us about the arguments your
examples?	son/daughter has?
	Have you noticed if your son or daughter is
	more/or less argumentative since
	participating in the programme? How so?
	Why do you think they are less/more
	argumentative?
	Have you noticed any changes in the way your
	son/daughter talks to you about their

	feelings? Their needs?
	Do you think this could have prevented
	arguments?
Since participating in the programme, have you noticed any changes in [NAME] in terms of their	What were the changes?
friends and friendships?	How did these changes affect [NAME]'s mood
	and behaviour?
Sometimes we do things to help us cope with our feelings (like when we feel angry, sad or worried).	Give examples - Going out for a walk, drawing,
Doing these things helps us to feel calm and feel better. Did you notice [NAME] do things to feel	meeting friends, or other things could be used
better?	to change one's negative feelings. Did you
	notice [NAME] do such things? Have you
	noticed them doing more or less of these
	things since participating in the programme?
We all face problems in life, regularly. We might have financial, health, school-related problems. Did	What do you think about this? Do you have
you notice any changes in [NAME]'s ability to solve problems in life?	any examples of problems that [NAME] has
	solved since participating in the programme?
We sometimes lose hope about our future and our future feels dark and bleak. Other times we feel	Were they more or less hopeful about life?
more hopeful that our future will be good and bright. Did you notice any change about how [NAME]	How can you tell?
talks about the future since they have been in the programme?	
Unintentionally it's possible the programme had some negative effects. Do you think the	For [NAME]? For your family?
programme had any negative effects?	E.g. 1) Preventing kids from working or helping
	with chores, or homework, so being
	burdensome 2) Making the kids feel labelled,
	bardensome 2) waking the kias reer labelled,

	discriminated against 3) Talking or thinking about problems made them feel worse/more fragile. 4) Kids pick up negative habits from peers.
Context of IPT	
Now we want to hear from you about who you think can and who can't benefit from a programme like this.	-
Do you think, all adolescents from all backgrounds can benefit from the programme?	Girls/boysHigh SES/Low SESOlder/younger
Can you think of any kinds of adolescents who wouldn't be helped? Why wouldn't they be helped?	-
Now I want to ask about your adolescent's school. How did the school support [NAME] to participate in IPT? Can you give examples?	- Were they supportive or unsupportive, or both? Why?

School principal/teacher/school nurse SSI topic guide (implementation and CMOs – indirect)

THEMES	PROBES
Icebreaker: Thank you for agreeing to be interviewed. We have been doing a programme in your school to	
help adolescents with heart-mind problems. This is the first time running such a programme in Chitwan so	
we are interested to hear what you think about it and how we can improve it. Please be open with us. There	
are no right or wrong answers. Your experience is very important which is why we are here today.	
ICEBREAKER	
To start with, please tell us a little bit about yourself and your work as a School principal/teacher/school	
nurse.	
What do you enjoy about your job? Why?	
What are the main challenges of your job?	
We have been working with adolescents with heart mind problems. Do you ever come across such	
adolescents in your work as a School principal/teacher/school nurse?	
Trial Implementation	
Now I want to ask you some questions about the programme we have been running in your school.	
Can you tell us about your experience of the groups ?	How did you come to know about
	them?
	What is your impression of the
	groups?
	What did other staff members
	think about the groups? Why?

What did you like about the program? What encouraged you (or would encourage you) to support the	
program?	
What did you not like about the program? What discouraged you from supporting these groups in schools?	
What could we do differently to improve our program?	- Recruitment, surveys, treatment
IPT and CMOs (mechanism and context)	-
Now, we would like to ask more specific questions about your observations on how the program helped or	
did not help. First, do you know any students who participated in the IPT program? Do you remember their	
names [write down their NAMES. If they don't know any student in particular, the questions will have to be	
asked more broadly about the school]?	
When you think about [NAMES or STUDENTS in school generally], did you see any changes in them, since	Improved mood
the program started? Do you have an example?	Improved social functioning and
	school functioning (attendance,
	grades)
What type of changes did you see in those students?	1) Reducing conflict with parents,
	peers, teachers, 2) Making them
	feel more capable in life, 3)
	Making them feel more hopeful,
	4) Support from the others in the
	program, 5) Better social support
	reduced isolation in general 6)
	Manage emotions better

	1
Was the programme harmful in any way in your school? Can you give a specific example? What was the	1) Preventing kids from working or
negative impact of the programme on this student, or other students?	helping with chores, or
	homework, so being burdensome
	2) Making the kids feel labelled,
	discriminated against 3) Talking or
	thinking about problems made
	them feel worse/more fragile. 4)
	Kids pick up negative habits from
	peers.
What kind of students do you think would benefit from attending these groups?	Boys? Girls? What kind of
Are there any students you don't think would benefit from attending these groups?	problems?
	Rich versus poor
Do you think the program would help girls and boys differently? Why so?	
Do you think the program would help adolescents from rich families and poor families differently? Why so?	
Role of the school environment	
In the future we want to implement this programme in other schools. What kinds of schools will be best for	
us to work in? Why?	
We are now coming to the end of our discussion. Thank you for talking to us. One last question for you. Is	
there anything else you would like to tell us about adolescent mental health and your role as school staff?	

IPT Facilitators FGD on CMOs (n=1, 7 facilitators, + 2 clinical supervisors P and P)

THEMES	PROBES
Thank you for agreeing to join this group discussion. We would like to hear about your experience of	
facilitating IPT. In this discussion we want to focus on what it was like for you working with adolescents	
from different backgrounds and in different schools	
Please be open with us. There are no right or wrong answers and we will not be offended if you tell us	
anything negative about IPT. Your experience is very important which is why we are here today.	
Start with an explanation about and definitions of context, mechanisms and outcomes, using diagrams	
to help.	
	-
Mechanisms	
Now I would like to start by talking about mechanisms and how you think IPT helps adolescents.	-
To start with can you tell us which parts of IPT you think are most helpful for reducing depression in	Strategies/techniques, sick role, linking
adolescents?	mood with problem area,
	communication analysis, problem
	solving, linking mood with events, etc.
You mentioned [strategy mentioned in the previous question] works to reduce depression. Now, we	Reducing conflict (parent, sibling,
would like to understand "how" [strategy] reduce depression. Can you explain, how do you think it	friend, partner), feeling more hopeful,
works?	feeling more competent (self-efficacy),
To illustrate this, imagine you take an antacid pill for your stomach pain. It does not magically reduce	managing emotions (emotion
the pain, it reduces pain through reducing the acidity in your stomach, and that's how it reduces the	regulation), support (social support)

pain. Similarly, we assume, [strategy] would not reduce depression directly, but it would reduce	
depression, because it helps adolescents in some ways.	
Make a slide/flipchart listing their answers	
Context	
What do you think about this statement: "IPT helps some adolescents but not all"?	
In your experience, who in your IPT groups benefited most?	Why? Males/females, younger/older,
	poor/rich, adversity, supportive
	parents, severe depression
Who benefited least?	Same as above
Gender and IPT	
Context: For boys who do not experience cultural norms or structural violence which impede opportunities	
to implement new strategies.	
Mechanism: IPT enables participants to participate in discussions through which they learn strategies to	
develop hope, reduce conflict, build relationships and improve self-efficacy.	
Outcome: This generates reductions in depression	
What about IPT is helpful for girls?	Strategies/techniques, sick role, linking
	mood with problem area,
	communication analysis, problem
	solving, linking mood with events, etc.

What are the most helpful parts of IPT for boys?	Same as above
What is not helpful about IPT for girls? Why?	Obtaining consent, attending sessions,
	participating in discussions, doing
	experiments at home, sharing
	problems, giving and receiving support
	from group members, support from
	family members
What is not helpful about IPT for boys? Why?	Same as above
Now let's focus on the mechanisms of IPT and whether the same mechanisms are important for boys	
and girls. What do you think? (show slide/flip chart with mechanisms listed above)	
Age	
Context: For older (and more cognitively able?) students more cognitively able to consider others'	
perspectives, learn negotiation skills, develop solutions to interpersonal problems, understand links	
between events and mood, manage anger and name and express emotions.	
Mechanism: IPT enables participants to participate in discussions through which they learn strategies to	
develop hope, reduce conflict, build relationships and improve self-efficacy.	
Outcome: This generates reductions in depression.	
Now we want to ask about your experience of working with older and younger adolescents. In your	Why?
opinion, who benefitted more? Older or younger?	
What are the most helpful parts of IPT for younger kids?	Strategies/techniques, sick role, linking
	mood with problem area,

	communication analysis, problem
	solving, linking mood with events, etc.
What are the most helpful parts of IPT for older kids?	Same as above
What do younger kids find difficult about IPT?	Obtaining consent, attending sessions,
	participating in discussions, doing
	experiments at home, sharing
	problems, giving and receiving support
	from group members, support from
	family members
What do older kids find difficult about IPT?	Obtaining consent, attending sessions,
	participating in discussions, doing
	experiments at home, sharing
	problems, giving and receiving support
	from group members, support from
	family members
Now let's focus on the mechanisms of IPT and whether the same mechanisms are important for older	
and younger kids. What do you think? (show slide/flip chart with mechanisms listed above)	
Financial precarity and adversity	
Context: For students of higher socioeconomic status not experiencing structural vulnerability or	
intractable adversity and having more opportunities to implement new strategies.	
Mechanism: IPT enables participants to participate in discussions through which they learn and	
implement strategies to develop hope, reduce conflict, build relationships and improve self-efficacy.	

How?
Ask for examples
How?
How did they do in the groups?
Can IPT help these kids? How?
How did they do in the groups?
Can IPT help these kids? How?
Why/Why not? What does a
supportive family look like?

Context: For students in schools with school climates characterised by strong student-staff and student-	
Context. For students in schools with school chimates characterised by strong student-stan and student-	
student relationships and norms of mutual respect and social support and thereby having more	
opportunities to implement new strategies.	
Mechanism: supportive for implementation or amenable for adolescents to implement ipt skills	
Outcome: This generates reductions in depression.	
Now we want to focus on schools and how they influence the way in which IPT works. Can you tell me	Staff? Students?
about your experience of schools supportive of the adolescents in your groups?	What did they do?
	What was the outcome?
Schools can also be unsupportive. Can you tell me about your experience of unsupportive schools?	Why were they unsupportive?
	How did this affect the adolescent?
	What was the outcome?
Considering the mechanisms we listed earlier, in unsupportive schools which of these mechanisms will	
work? Which mechanisms won't? Why?	
What can schools do to make sure these mechanisms are working?	- Staff, students
Finishing	
We are now coming to the end of our discussion. Thank you for talking to us. One last question for you.	
Is there anything else you would like to tell us about your experience of IPT?

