- secondary qualitative analysis of interview transcripts with participants and facilitators in the uncontrolled feasibility study of group IPT for adolescents in Sindupalchowk.

The project team reviewed and revised the theory of change. Figure 2 presents the most recent version. It includes roles for facilitators (delivering therapy and managing groups), school staff and caregivers (supporting adolescents), and adolescents (attending and participating in group sessions). Intervention mechanisms incorporate social learning theory (adolescents acquire communication skills - sharing, listening, giving feedback, and negotiating), attachment theory (adolescents identify and evaluate key interpersonal relationships), mental health literacy (adolescents understand depression is common and can be treated) and problem-solving [17, 18]. Through these mechanisms, adolescents perceive the possibility of an improvement in their interpersonal circumstances and mood, internalise their membership of the IPT group (social identity theory), and improve their ability to empathise and communicate their interpersonal needs (emotion validation) [19]. These mechanisms generate intermediate impacts (relationship initiation and/or

improvement, conflict reduction, perception of hope, self-efficacy and emotion regulation) which in turn generate a reduction in depressive symptoms and improvements in general functioning.

Research aims and questions

We aim to assess the feasibility and acceptability of delivering group IPT in secondary schools in Chitwan Nepal, as well as the feasibility and acceptability of trial procedures. We will address the following research questions:

- Is it feasible to deliver IPT in secondary schools in Chitwan?
- Is the intervention acceptable to participants?
- Is the intervention acceptable to caregivers and teachers?
- Is it feasible to train local lay people to deliver IPT?
- Are trial procedures (randomisation, masking, data collection, safety standard operating procedures, control conditions) feasible to implement and acceptable to participants and schools?
- How reliable are the measures for trial outcomes?
- What are the recruitment, retention and response rates for trial participants?
- How does context affect implementation of IPT?
- Do data from the process evaluation support or refute CMOCs?
- What are the costs per participant of implementing IPT in schools in Chitwan?

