Mechanism: IPT enables participants to participate in discussions through which they learn and implement strategies to reduce conflict and build relationships.

Outcome: This generates reductions in depression.

CMOC 3

Context: For boys who do not experience cultural norms or structural violence which impede opportunities to implement new strategies.

Mechanism: IPT enables participants to participate in discussions through which they learn strategies to develop hope, reduce conflict, build relationships and improve self-efficacy.

Outcome: This generates reductions in depression.

CMOC 4

Context: For older (and more cognitively able?) students more cognitively able to consider others' perspectives, learn negotiation skills, develop solutions to interpersonal problems, understand links between events and mood, manage anger and name and express emotions.

Mechanism: IPT enables participants to participate in discussions through which they learn strategies to develop hope, reduce conflict, build relationships and improve self-efficacy. Measure cognitive ability to understand and apply skills (knowledge quiz) – could also consider a self assessment of skills

Outcome: This generates reductions in depression.

CMOC 5

Context: For students participating in initial sessions and participating in discussions which validate participants' experiences and instil hope.

Mechanism: IPT enables participants to develop hope and motivation to engage in the intervention.

Outcome: This generates immediate reductions in depression.

We will refine the CMOCs by analysing qualitative and quantitative process evaluation data. Table 5 lists these data. In addition to data collected through the trial and process evaluation we will also conduct semi-structured interviews with 30 adolescents (20

depressed and 10 non-depressed) from schools which are not participating in the trial. In these interviews we will specifically explore themes from the CMOCs including age, gender, socioeconomic status and school climate and how they influence adolescents' experiences of depression.

Cost analysis

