CMOC 5 Context: For students participating in initial sessions and participating in discussions which validate participants' experiences and instil hope. Mechanism: IPT enables participants to develop hope and motivation to engage in the intervention. Outcome: This generates immediate reductions in depression.	Analysis of SSI and FGD transcripts with participants and facilitators probing on CMO	Exploring temporal relationship between hope and PHQ-A score by plotting baseline, midline and endline data.

Table 5: Process evaluation data collection in the intervention arm

Method	Timing	Process indicator
Quantitative attendance data collected by IPT facilitators at each group session	Throughout intervention	Dose
Intervention fidelity data collected using the IPT checklist by clinical supervisors	For each group: 1 observation in the initial phase, 2 observations in the middle phase and 1 observation of the termination phase (4 per group)	Fidelity
Unstructured observation by clinical supervisors – field notes about IPT sessions and informal conversations	For each group: 1 observation in the initial phase, 2 observations in the middle phase and 1 observation of the termination phase (4 per group)	Fidelity, context, mechanism
Transcripts of IPT group sessions	For each group: 1 observation in the initial phase, 2 observations in the middle phase and 1 observation of the termination phase (4 per group)	Mechanism
Notes on supervisory meetings between clinical supervisors and facilitators	Throughout intervention	Fidelity, mechanism
Facilitator competency data collected using ENACT and GroupACT	Pre-training, post training (ENACT and GroupACT), in-vivo (initial, middle and termination group sessions (GroupACT only in parallel with IPT checklist)	Fidelity, mechanism
Interviews with participants (n=20)	Spread interviews over endline and follow-up	Context, mechanism
Group discussion with facilitators (n=2)	Endline	Fidelity, context, mechanism
Interview with school teachers/principals	Endline	Context, mechanism
Interview with school staff – school nurses, school principals, teachers (n=17-20)	Endline	Context, mechanism
Interview with caregivers (n=10)	Endline	Context, mechanism
Midline quantitative surveys with IPT participants to measure intermediate outcomes	After group session 2 and 6	Mechanism

Figures

[figure not shown]

Figure 1: Overall programme of work

[figure not shown]

Figure 2: Interpersonal therapy theory of change

[figure not shown]

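### The adolescent topic guide's one timing question for CMOC 5 presupposes improvement, which biases answers away from no change or early worsening without excluding them

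*Protocol*

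**What the plan says.** The CMOCs section and Table 4 state the CMOC 5 outcome as: "Outcome: This generates immediate reductions in depression". Under Research aims and questions, one pilot question is: "Do data from the process evaluation support or refute CMOCs".

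For CMOC 5, Table 4 names two strands of evidence:

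- Qualitative: "Analysis of SSI and FGD transcripts with participants and facilitators probing on CMO". Caregivers are not listed, although Table 4 does list them for CMOCs 3 and 4.
- Quantitative: "Exploring temporal relationship between hope and PHQ-A score by plotting baseline, midline and endline data".

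In Appendix A, the adolescent guide raises timing once, at the end of its block on benefit mechanisms. It reminds the participant of the sequence of sessions ("group, then 10 group sessions. I am curious, when did you start") and goes on: "feeling better? Was it after the first session, or towards the end" of the groups. The accompanying probe asks whether this came once the participant could talk about their problem area.

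The caregiver guide asks when changes were seen, with a probe that runs in both directions: "Did you see benefits (or harm) after the" pre-group sessions, the first few sessions or later ones. The Process evaluation section describes the appended guides as drafts.

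**The concern.** CMOC 5 differs from the other CMOCs mainly in its claim about timing: that benefit comes early. If interview data are to support or refute it, the question that elicits timing should be as open to a participant who felt nothing, or felt worse, as to one who felt better.

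This question takes improvement as given and asks only for its date. A participant who did not improve is nudged to name a time anyway. If the time named is the first session, the answer may be coded as support for CMOC 5. The pilot is meant to refine the CMOCs before the phase III trial tests them, so a lean of this kind could be carried forward.

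**Working it through.** No arithmetic applies. The check was to read every question in the four appended guides for content on the timing of change, and to compare the result with the CMOC 5 sources in Table 4.

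| Appended guide | Questions on timing of change | Direction allowed by the wording | Listed source for CMOC 5? |
|---|---|---|---|
| Adolescents | 1 | Improvement only | Yes |
| Facilitators (focus group) | 0 | Not applicable | Yes |
| Caregivers | 1 | Benefit or harm | No |
| Principals, teachers, nurses | 0 (asks about changes since the programme began, not when they occurred) | Not applicable | No |

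**Adolescent question.** No filter asks whether anything changed. The preceding questions in the block ask what IPT helped with and how it helped, so the timing question arrives after a run of prompts about benefit. The two timings offered are early improvement and late improvement. The probe then suggests a cause for the improvement.

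**Facilitator focus group guide.** It covers general mechanisms, gender, age, financial precarity and adversity, and school climate. Beyond the general opening, these sections match CMOCs 3, 4, 1 and 2. Nothing matches CMOC 5, and nothing asks when change occurred.

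**Caregiver guide.** Its probes on change mention both getting better and worsening, and its timing probe mentions benefits or harm. The team therefore had a two-directional form available, but it sits in the guide whose respondents are not listed for CMOC 5. It still assumes some change, so a neutral version also needs a no-change option.

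**What else could reveal no change or worsening.** After the timing question, the adolescent guide turns to harm. It asks what was unhelpful and then says the team wants "to understand this better. What type of negative effects do you" think it had. Later it asks whether some group members failed to benefit. None of these asks when. Separately, PHQ-A and hope are measured at baseline, both midlines, endline and follow-up (Table 3), and Midline 1 falls after the second group session (Design). Plots of those scores can show a flat or worsening early course.

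**Reach.** The question applies to every adolescent interviewed with this guide. Table 5 gives 20 participant interviews and the Process evaluation text gives six individual adolescent interviews, so the reach is 6 to 20 depending on which figure applies.

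**The case against.** A reader might infer that the question cannot yield evidence of no change or worsening, and so that the interview evidence can never count against CMOC 5. The document does not support that reading, for four reasons.

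- An answer placing improvement towards the end of the groups contradicts the word *immediate*, which is the distinctive part of CMOC 5.
- This is a topic guide, not a closed questionnaire. It opens by saying that there are no right or wrong answers and that negative comments will not offend. A participant can reject the premise.
- The same interview goes on to harm and non-benefit.
- The PHQ-A and hope plots form a separate strand, and they date an early change better than recall does.

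These points stand, and they limit the finding to bias. They do not remove it. The harm and non-benefit questions carry no timing, so they do not show whether a participant felt no change or felt worse after the initial sessions. The plots do not correct the interview strand, which Table 4 lists in its own right.

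A second inference would be that the process evaluation has no neutral timing probe for CMOC 5 anywhere. That cannot be shown either. The guides are drafts, and the Process evaluation section also plans facilitator interviews and adolescent focus groups, for which no separate guides are appended. The finding is confined to the guides that are shown.

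It can also be said that probing directly on a CMOC is a declared method: Table 4 mentions direct and indirect probing for CMOC 1. Direct probing does not require wording that assumes the answer.

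**Conclusion.** The point holds as one of wording. In the appended adolescent guide, the only timing question relevant to CMOC 5 presupposes improvement, so it makes reports of no change or early worsening less likely without ruling them out. The appended facilitator focus group guide, the other listed source, has no timing question to offset this.

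The severity is low. The protocol gives no basis for quantifying the bias. None of the progression criteria in Table 2 and none of the planned quantitative analyses depends on the question. What is affected is how much weight the interview strand can bear when CMOC 5 is judged or refined. The conclusion assumes that interviewers put the question broadly as written and that the draft guides shown are the ones used.

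**What to change.** In the adolescent guide, replace the timing question with a neutral one that follows the caregiver guide's two-directional approach and adds a no-change option, for example: *Did you notice any change in how you felt during the programme: better, worse or no change? If so, after which session?* Put the same question, asked about the adolescents in their groups, into the facilitator focus group guide.

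The cost is one reworded line and one added line, with no extra interviews. There is a small downside. The Trial status section reports that by July 2024 the groups had finished and the endline and follow-up surveys were under way, while Table 5 spreads participant interviews over those two points, so some interviews may already have used the existing wording. Record which version each interview used, and read answers to the existing wording with its lean in mind. Whatever the state of the pilot interviews, carry the neutral wording into the phase III guides.
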